4.6.1 Treatment

For each treatment, subjects will undergo bronchoscopy under general anesthesia or moderate sedation, at the discretion of the bronchoscopist. During both procedures, subjects will be treated with Coils according to the Instructions for Use. Subjects will receive prophylactic drugs pre-procedure and post-procedure.

Following LVRC placement (Visit 2), the subject will remain in the hospital under observation per standard hospital practice. Following hospital discharge, the subject will be contacted by phone one week after Visit 2 and will be seen at the study site at one month after Visit 2. After the one month visit following Visit 2, the subject will be scheduled for the second LVRC placement in the contralateral lung to take place approximately 2 months after Visit 2. Only a single lung will be treated during any bronchoscopy.

After the subject's second LVRC placement procedure (Visit 5), the subject will remain in the hospital under observation per standard hospital practice. Following hospital discharge, the subject will be contacted by phone one week after Visit 5 and will be seen for the tests, procedures and follow-up described in Table 6. Subjects will be followed up annually for 5 years. After the 5 year visit, the subject will exit the study.

Table 6. Visit Schedule

Procedure / Assessment	Visit 1 Pre-Treatment (Screening)	Visit 2 LVRC Placement #1	Visit 3 1 Week post Visit 2 ^a (Phone Call)	Visit 4 1 Month post Visit 2 ^b (Office Visit)	Visit 5 LVRC Placement#2 (2 Month post Visit 2)	Visit 6 1 Week post Visit 5 ^a (Phone Call)	Visit 7 1 Month post Visit 5 ^b (Office Visit)	Visit 8 6 Months post Visit 2 ^c (Office Visit)	Visit 9 9 Months post Visit 2 ^a (Phone Call)	Visit 10 12 Months post Visit 2 ^c (Office Visit)	Visit 11 24 Months post Visit 2 ^c (Office Visit)	Visit 12 36 Months post Visit 2 ^c (Office Visit)	Visit 13 48 Months post Visit 2 ^c (Office Visit)	Visit 14 60 Months post Visit 2 ^c (Office Visit)
Informed Consent	X													
Inclusion/ Exclusion	X													
Focused physical exam including vital Signs andSpO ₂	X	X		X	X		X	X		X	X	X	X	X
Record the following measures from the 12 Month RENEW Visit in the eCRF as baseline measurements: Spirometry, Lung Volumes and Diffusing Capacity, 6MWT, SGRQ, mMRC*		X												
Spirometry	X							X		X	X	X	X	X
Lung Volumes and Diffusing Capacity	X*							X		X	X	X	X	X
6MWT	X*			X			X	X		X	X	X	X	X
SGRQ	X*			X			X	X		X	X	X	X	X
mMRC	X*			X			X	X		X	X	X	X	X

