7.1 Serious Adverse Events

In accordance with 21 CFR Parts 803 and 812, a Serious Adverse Event (SAE) is defined as any untoward medical occurrence that:

1. results in death,
2. is life-threatening,
3. requires inpatient hospitalization or prolongation of existing hospitalization,
4. results in persistent or significant disability/incapacity,
5. is a congenital anomaly/birth defect, or
6. requires intervention to prevent permanent impairment or damage.

In addition, Major Complications, as defined below (which will be adjudicated by the Medical Monitor based on AE/SAE documentation in the eCRFs):

- Death;
- Pneumothorax that requires a chest drainage tube for more than 7 days (from time of chest drainage tube insertion to the time of chest drainage tube removal);
- Hemoptysis requiring an intervention (e.g., blood transfusion(s), arterial embolization, or surgical/endoscopic procedure);
- COPD exacerbation that becomes life-threatening or disabling as a result of an increase in respiratory symptoms requiring in-patient hospitalization of >7 days with or without mechanical ventilation;
- Lower Respiratory Infections (including pneumonia) defined by new or increased clinical symptoms such as fever, chills, productive cough, chest pain, dyspnea or an infiltrate on plain chest x-ray and hospitalization for administration of intravenous antibiotics and/or steroids;
- Respiratory failure defined as a requirement for mechanical ventilatory support (whether via endotracheal tube or mask) for >24 hours; and
- An unanticipated bronchoscopy in order to remove one or more Coils due to a device-related AE. (Note: This definition does not include re-positioning, replacement or removal of the Coil(s) during the procedure.)

All SAEs must be reported to the PneumRx Clinical Affairs immediately (within one working day) using the AE eCRF. To maintain subject confidentiality, the subject shall only be identified by the subject number used on the eCRFs. Further written reports through final resolution of the event, study completion or termination or, in case of permanent impairment, until the event stabilizes and the overall clinical outcome has been ascertained shall be provided to PneumRx, Inc. Clinical Affairs via the eCRF.

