A Coil(s) may be removed up to 2 months following the treatment for medically indicated safety reasons (e.g., due to a persistent air leak or poor Coil location that may pose a safety risk). Other than during the LVRC treatment procedures (Study Visits 2 and 5), Coils should only be removed or repositioned for safety reasons, and Coils may not be replaced post-procedure. If the decision is made to remove a Coil(s), refer to the "Coil Removal Instructions" section in the Instructions for Use for details. The Investigator will notify the Sponsor of the need for removal prior to removing any Coil(s) and return the Coil(s) to PneumRx Quality Assurance for inspection.

In prior PneumRx OUS Feasibility Studies, numerous Coils have been bronchoscopically repositioned or removed during treatment procedures to improve placement or to deploy a different size Coil. All attempts to remove or reposition Coils during the over 200 procedures performed in the OUS studies have been successful and easy to perform as determined by the Investigator. There have been no reported complications or adverse events associated with the bronchoscopic removal or repositioning of the Coils during the LVRC procedures.

Coil(s) can and may be repositioned, replaced or removed during the treatment procedure (Study Visits 2 and 5). Coils can be removed bronchoscopically up to 2 months after the LVRC procedure, but only if medically indicated. Such medically indicated post-procedure removal would be considered a Major Complication, and will be recorded in the eCRF AE page. Although Coils have been removed as late as 4 months post-procedure in animal studies, the need to remove Coils in human trials is not anticipated based on safety data from European clinical trials. Note that the Coil removal procedure has not been tested after time periods longer than 4 months post-procedure.

- **Pneumothorax**

Pneumothorax is defined as the presence of air within the pleural space, which may or may not require chest tube insertion. There is also an increased risk of pneumothorax in patients with emphysema over those who do not have emphysema (Guo, 2005).

- **Reaction**

Reaction to the study device, including (1) an allergic reaction to the metal (nickel-titanium) that may require removal of the study device, and (2) an opacity on chest x-ray that may be difficult to differentiate from infectious pneumonia.

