1.2.2 Safety Endpoints

The primary safety analysis will tabulate subjects who experience one or more major complication(s) within 12 months post-baseline (and within defined blocks of time post-baseline). Major complications will be determined/adjudicated by the Clinical Events Committee.

Major Complications:

- Death;
- Pneumothorax that requires a chest drainage tube for more than 7 days (from time of chest drainage tube insertion to the time of chest drainage tube removal);
- Hemoptysis requiring blood transfusion(s), arterial embolization, or surgical/endoscopic procedure;
- COPD exacerbation that becomes life-threatening or disabling as a result of an increase in respiratory symptoms requiring in-patient hospitalization of >7 days with or without mechanical ventilation;
- Lower Respiratory Infections (including pneumonia) defined by new or increased clinical symptoms such as fever, chills, productive cough, chest pain, dyspnea and an infiltrate on plain chest x-ray and hospitalization for administration of intravenous antibiotics and/or steroids;
- Respiratory failure defined as a requirement for mechanical ventilatory support (whether via endotracheal tube or mask) for >24 hours; and
- An unanticipated bronchoscopy in order to remove one or more Coils due to a device-related AE. (Note: This definition does not include re-positioning, replacement or removal of the Coil(s) during the initial placement procedure.)

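### The Coil-removal Major Complication is defined by an unplanned bronchoscopy, so surgical removal for device harm is not covered and removal at Visit 5 is classified inconsistently

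*SAP*

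**What the plan says.** The primary safety result in SAP 1.2.2 is a tabulation of subjects with at least one Major Complication in the 12 months after baseline. One item in the list of Major Complications is "An unanticipated bronchoscopy in order to remove one or more Coils due to a device-related AE". Protocol 7.1 has the same item.

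Each document adds a note on what the item leaves out, and the notes differ:

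- SAP 1.2.2: "This definition does not include re-positioning, replacement or removal of the Coil(s) during the initial placement procedure".
- Protocol 7.1: "This definition does not include re-positioning, replacement or removal of the Coil(s) during the procedure".

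Protocol 9.1 discusses Coil removal separately. It allows adjustment or removal during the two treatment sessions, Visits 2 and 5. It then says "Coils can be removed bronchoscopically up to 2 months after the LVRC procedure, but only if medically indicated", and follows with "Such medically indicated post-procedure removal would be considered a Major Complication, and will be recorded in the eCRF AE page". Under its heading on reactions, 9.1 lists "an allergic reaction to the metal (nickel-titanium) that may require removal of the study device", without a route or a time.

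Visit 5 is a planned bronchoscopy. Protocol 4.6.1 says that "the subject will be scheduled for the second LVRC placement in the contralateral lung to take place approximately 2 months after Visit 2".

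**The concern.** When an implant has to come out because it harmed the subject, that is a direct sign of a safety failure, whichever way it is taken out. The item instead asks two further questions that have nothing to do with harm: was it a bronchoscopy, and was that bronchoscopy unplanned? A case that fails either question can drop out of the primary safety tabulation although the device caused the event.

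The study is single-arm and descriptive (SAP 1.2 and 1.4), so this tabulation is itself the main safety statement. Omitted removals can only lower the rate, which favours the device. Where two passages classify the same removal differently, the count also depends on which passage the adjudicator follows. The documents do not agree on who that is: Protocol 7.1 names the Medical Monitor and SAP 1.2.2 the Clinical Events Committee.

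**Working it through.** The plan states no removal rate, sample size or expected complication rate, so there is no figure to reproduce. The check is to run four cases through the three passages. In every case the cause is taken to be a device-related adverse event and no other listed event occurs.

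| Case | SAP 1.2.2 | Protocol 7.1 | Protocol 9.1 | Result |
|---|---|---|---|---|
| A. Coil removed surgically | Not a bronchoscopy: not met | Same: not met | Its Major Complication sentence refers back to bronchoscopic removal: not reached | Not counted |
| B. Visit 2 Coil removed at Visit 5 | Bronchoscopy was scheduled, so literally not met; the note does not naturally exclude it | Literally not met; the note can be read to exclude it | Bronchoscopic, about 2 months on, after the procedure that placed it: arguably a Major Complication, yet removal at Visit 5 is also treated as part of treatment | Inconsistent |
| C. Unplanned bronchoscopic removal, at any time | Met | Met | Covered up to 2 months | Counted |
| D. Coil removed in the session that placed it | Excluded by the note | Excluded by the note | Allowed as part of treatment | Not counted, as intended |

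**Case A.** No item in either list names surgical removal of a Coil. The hemoptysis item in the same list names surgical as well as endoscopic procedures, so both routes are spelled out there and only one here.

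**Case B.** The conflict has three parts. The main clause requires an unanticipated bronchoscopy, which Visit 5 is not. The two notes carve out different things: the Protocol note could cover any treatment session, while the SAP note covers only the initial placement. Protocol 9.1 makes medically indicated removal after the procedure a Major Complication without requiring the bronchoscopy to be unanticipated. Two careful adjudicators could therefore decide the same case differently.

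**Case C.** Neither version of the item has a time limit. The 2-month limit in 9.1 concerns when Coils may be removed, not what is counted.

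**Size.** Let x be the number of subjects with at least one Major Complication when all removals for device-related events are counted, and k the number whose only qualifying event is a removal of type A or B that goes uncounted. The full rate is x/N, the reported rate is (x − k)/N, and the difference is k/N. N is not given, so it is an assumption here. For k = 1:

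- N = 50: 1/50 = 2.0 percentage points
- N = 150: 1/150 = 0.7 percentage points

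Only removals in the first 12 months affect the primary rate. Later ones affect the Major Complication summaries by follow-up period (SAP 2.3.2 and 2.3.2.3).

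**The case against.** The strongest reply is that the gap is narrow and largely hypothetical.

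- **Surgical removal is never mentioned.** Protocol 9.1 does not expect removals to be needed, and exclusion criterion 19 keeps out subjects with a known nitinol sensitivity. The allergy text is a risk statement, not a rule on removal. This stands: Case A is an omission, not a stated exclusion, and such cases should be few.
- **Other items catch some of these subjects.** Death, prolonged chest drainage, hemoptysis needing a procedure, a qualifying infection or ventilation beyond 24 hours would each put the subject in the tabulation. This also stands, and it limits the loss to subjects with removal alone.
- **Visit 5 treats the other lung.** Nothing describes going back into the first lung at that session, and 9.1 describes removals during treatment as adjustments to placement. So Case B is probably uncommon. The inconsistent wording remains.
- **The events stay visible elsewhere.** Surgery with an inpatient stay is a serious adverse event, and such events are tabulated and listed. That does not return the case to the primary tabulation. The listing fields in SAP 2.3.2.3 show neither that a Coil was removed nor by which route.
- **Adjudication may resolve it.** Adjudicators apply the written definition, and no charter is available to show how these cases would be handled.

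A reader might go further and infer that, because 9.1 ends bronchoscopic removal 2 months after each procedure, no removal can be counted after about month 4 and the 12 to 60 month tables cannot show late removals. The documents do not support that. The item has no time limit, so a late unplanned bronchoscopic removal still meets it. The share of follow-up lying beyond the 9.1 window is a share of calendar time and says nothing about the share of events missed. Nor do the documents support saying that Visit 5 removals are plainly excluded: the passages conflict.

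**Conclusion.** The concern holds in a limited form. A surgical removal for a device-related adverse event falls outside the Coil-removal item, and the subject is missed unless another item is met. For a Visit 2 Coil removed at Visit 5, SAP 1.2.2, Protocol 7.1 and Protocol 9.1 do not give one answer.

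Any undercount favours the device and is probably small. The 0.7 to 2.0 percentage points per removal-only subject rests on an assumed N of 150 to 50; the number of such subjects cannot be estimated from the documents. No formal test depends on the item. The case for changing it is that the remedy is cheap and the error can run in only one direction.

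**What to change.** In SAP 1.2.2 and Protocol 7.1, replace the item with: removal of one or more Coils by any route, at any time after the end of the procedure in which that Coil was placed, due to a device-related adverse event. Use one note in both documents that excludes only repositioning, replacement or removal during the procedure in which that Coil was placed. Align this with the Major Complication sentence in 9.1, so that a Visit 2 Coil removed at Visit 5 for a device-related event counts. Record the route and date of removal on the adverse event form. If comparison with results under the plan's present definition is wanted, tabulate the item both ways.

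This changes only what is counted. It leaves untouched when, whether and how Coils are removed.

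The cost is a small amendment to both documents, a small addition to the form (with a look back at removals already recorded, since SAP 1.4 describes enrollment in the past tense), and a rate that may be slightly less favourable.

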1.3 Analysis Populations

1.3.1 Intent-to-Treat Population

The Intent-to-Treat (ITT) population will include patients who enrolled in the CROSSOVER study, regardless of whether or not treatment was attempted.

1.4 Sample Size and Power Calculation

The CROSSOVER Study was designed to provide an opportunity for qualifying Control subjects from the RENEW study to receive the LVRC treatment once their participation in the randomized phase of the RENEW study was complete; all qualifying subjects who wished to participate and met the enrollment criteria were enrolled. Thus, the study sample size was not based on a primary and null hypothesis, or power calculation and results will only be presented descriptively.

2. ANALYSIS CONSIDERATIONS

2.1 Subject Disposition

The number of subjects screened, enrolled and treated in the study will be presented. Additionally, the number and percentage of subjects who complete the study to 12 months, 24 months, 36 months, 48 months and 60 months, and who terminate the study prematurely (by visit), will be presented including reasons for premature termination.

2.2 Demographic and Baseline Characteristics

Demographic and baseline characteristics will be summarized. Baseline is defined as the last assessment evaluated prior to treatment. Demographic and baseline characteristics will be presented with summary statistics (sample size (N), mean, standard deviation (SD), median, minimum, and maximum) for continuous variables and frequency distributions for categorical variables.

2.3 Endpoint Analyses

2.3.1 Effectiveness Endpoint Analyses

Summary statistics will be provided for change in 6MWT, percent change in FEV1 (L), absolute change in SGRQ (total and individual domain scores), absolute change in RV (L), absolute change in VC and absolute change in RV/TLC from baseline to the 12 month follow-up visit.

Additionally, summary statistics will be provided for the change at each follow-up visit (24 months, 36 months, 48 months and 60 months).

Frequency distributions will be presented for the 6MWT, SGRQ, FEV1 and RV responder rates for each follow-up time period (12 months, 24 months, 36 months, 48 months and 60 months).

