There are several treatments available for emphysema including smoking cessation, medications, physical therapy, supplemental oxygen, and surgery. Emphysema can be treated with inhaled bronchodilators, inhaled corticosteroids, anticholinergics, theophylline, phosphodiesterase-4 inhibitors and supplemental oxygen. Emphysema patients are prone to exacerbations, usually due to respiratory infections, which are usually treated with antibiotics and/or systemic corticosteroids and frequently require emergency room visits and/or hospitalizations. Emphysema patients may undergo pulmonary rehabilitation exercises and training. There are also two surgical procedures available for treatment of severe emphysema: lung transplantation and lung volume reduction surgery (LVRS). Lung transplantation is a seldom used option because of the limited availability of donor lungs, low transplantation priority for emphysema patients relative to other rapidly fatal pulmonary diseases, and because of the advanced age of most emphysema patients. Lung Volume Reduction Surgery is major surgery that carries the risk of morbidity and mortality. Recently, less invasive bronchoscopic approaches have been developed and several approaches are being actively investigated in human clinical trials in Europe and the US.

The PneumRx RePneu Coil System (RePneu Coil) is designed to compress the areas of lung parenchyma most damaged by emphysema. This compression reduces air flow to treated portions of the lung allowing enhanced airflow to healthier untreated portions of the lung (Figure 1). The compression also reduces the volume of the hyperinflated emphysematous lung, resulting in lung volume reduction with improved diaphragmatic efficiency. Additionally, by gathering up the loose parenchyma of the most severely damaged segments, the Coil restores elasticity and recoil to the whole lung, improving expiratory flow rates, lessening small airway collapse with air trapping, and reducing dynamic hyperinflation. Because the Coil acts by a simple mechanical action these effects are achieved immediately in the presence or absence of collateral ventilation. This device is deployed using a minimally invasive approach using a simple catheter-based delivery system through a fiber-optic bronchoscope and requires no incision.

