5.2 Exclusion Criteria

Subjects will be excluded from the study if any of the following conditions apply:

1. Subject has severe homogeneous emphysema as determined by the Core Radiology Lab
2. Subject has co-morbidities that may significantly reduce subject's ability to improve exercise capacity (e.g. severe arthritis, planned knee surgery) or baseline limitation on 6MWT is not due to dyspnea.
3. Subject has a change in FEV1 >20% (or, for subjects with pre-bronchodilator FEV1 below 1 L, a change of > 200 mL) post-bronchodilator, unless investigator can confirm by other means that subject does not have asthma.
4. Subject has DLCO <20% of predicted.
5. Subject has severe gas exchange abnormalities as defined by:
PaCO₂ >55 mm Hg
PaO₂ <45 mm Hg on room air (High altitude criterion: PaO₂ <30 mm Hg)
6. Subject has a history of recurrent clinically significant respiratory infections, defined as 3 hospitalizations for respiratory infection during the year prior to enrollment.
7. Subject has severe pulmonary hypertension. If pulmonary hypertension is present, "severe" is defined by right ventricular systolic pressure >50 mm Hg via right heart catheterization and/or echocardiogram.
8. Subject has an inability to walk >140 meters (150 yards) in 6 minutes.
9. Subject has evidence of other severe disease (such as, but not limited to, lung cancer or renal failure), which in the judgment of the investigator may

compromise survival of the subject for the duration of the study.

10. Subject is pregnant or lactating, or plans to become pregnant within the study timeframe.
11. Subject has an inability to tolerate bronchoscopy under moderate sedation or general anesthesia.
12. Subject has clinically significant bronchiectasis.
13. Subject has giant bullae >1/3 lung volume.
14. Subject has had previous LVR surgery, lung transplantation, lobectomy, LVR devices or other device to treat COPD in either lung.
15. Subject has been involved in pulmonary drug or device studies within 30 days prior to this study, with the exception of the RENEW Study.
16. Subject is taking >20 mg prednisone (or equivalent dose of a similar steroid) daily.
17. Subject requires high level chronic immunomodulatory therapy to treat a moderate to severe chronic inflammatory autoimmune disorder.
18. Subject is on an antiplatelet (such as Plavix) or anticoagulant therapy (such as heparin or Coumadin) which cannot be stopped for seven (7) days prior to procedure.

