1.2.1 Effectiveness Endpoints

- 6MWT: absolute change from baseline at 12 months in the 6 Minute Walk Test
- 6MWT: responder analysis, comparing baseline to 12 months, responders defined as those with an improvement of ≥ 25 meters^[1]
- Forced Expiratory Volume in one second (FEV₁): percent change in FEV₁ results measured using spirometry, comparing baseline to 12 months
- Saint George's Respiratory Questionnaire (SGRQ): absolute difference in SGRQ total score comparing baseline to 12 months.
- SGRQ: responder analysis, comparing baseline to 12 months, responders defined as those with an improvement of ≥ 4 points^[2]
- SGRQ: absolute difference in individual domain scores comparing baseline to 12 months
- FEV1: responder analysis, comparing baseline to 12 months, responders defined as those with an improvement of $\geq 10\%$.
- Residual Volume (RV): absolute difference in RV measured using plethysmography, comparing baseline to 12 months^[3-5]
- RV: responder analysis, comparing baseline to 12 months, responders defined as those with an improvement (decrease) of .35L
- Vital Capacity (VC): absolute difference in VC measured using plethysmography, comparing baseline to 12 months
- Residual Volume/Total Lung Capacity (RV/TLC): absolute difference in RV/TLC measured using plethysmography, comparing baseline to 12 months^[6-8]

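### The SAP has no rule for effectiveness values measured after a later lung transplant, LVRS, lobectomy or other volume-reduction device, so a subject who had one could be scored as a Coil responder.

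*SAP*

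**What the plan says.** SAP 2.3.1 summarises change in 6MWT, FEV1, SGRQ and RV, and also "absolute change in VC and absolute change in RV/TLC from baseline to the 12 month follow-up visit". It then extends the change summaries: "summary statistics will be provided for the change at each follow-up visit (24 months, 36 months, 48 months and 60 months"). For responders, "Frequency distributions will be presented for the 6MWT, SGRQ, FEV1 and RV responder rates for each follow-up time period", again at 12, 24, 36, 48 and 60 months.

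The responder definitions in SAP 1.2.1 are thresholds on change from baseline and nothing else. An example is "6MWT: responder analysis, comparing baseline to 12 months, responders defined as those with an improvement of" at least 25 m. For RV the wording is "responders defined as those with an improvement (decrease) of .35L". The SGRQ and FEV1 thresholds are 4 points and 10%. SAP 1.3.1 defines one population, all enrolled subjects.

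The protocol deals with other lung procedures at entry. Exclusion 14 in Protocol 5.2 reads: "Subject has had previous LVR surgery, lung transplantation, lobectomy, LVR devices or other device to treat COPD in either lung". Protocol 2.2 (Clinical Need) states: "There are also two surgical procedures available for treatment of severe emphysema: lung transplantation and lung volume reduction surgery (LVRS"). On follow-up, Protocol 4.6.1 says: "Subjects will be followed up annually for 5 years".

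**The concern.** Exclusion 14 shows that the sponsor does not want another volume-reducing procedure mixed with the Coil when subjects enter. The same mixing can happen after entry, over five years, in subjects with severe disease for whom the protocol itself names surgical options. Nothing in the effectiveness analysis separates the two.

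The late visits are this study's evidence on durability, and there is no control arm in which the same procedures would also occur and partly cancel. It is plausible, though the documents do not say so, that subjects doing poorly after Coils are the ones more likely to have something else done. If so, a subject in whom the Coils failed could appear in the 24- to 60-month tables as a responder.

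**Working it through.** **Is there a rule anywhere?** These are the places where one could stand:

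- SAP 1.2.1 and 2.3.1: thresholds and visits only, with no condition on treatment received in between.
- SAP 1.3.1: all enrolled subjects; no per-protocol or as-treated set.
- SAP 2.1: tabulates reasons for early termination, but names no procedure that requires exit.
- SAP Appendix 4.1: date imputation, time windows for adverse event, medication and deviation records, and output format. None of it limits which effectiveness values count.
- Protocol 4.2.1: discourages changes to the drug regimen only.
- Protocol Table 6: records medications, oxygen use and adverse events; no field for later lung procedures is described.
- Protocol 5.2, item 14: previous procedures only.

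No passage bars, censors, exits or flags a later procedure. A literal program would use every value measured.

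**Responder rates.** Let N be the number measured at a visit, r the number scored as responders, and k the number among those r who qualify only on a post-procedure value. As written the rate is r/N. With the k subjects scored as non-responders it is (r − k)/N. The difference is k/N. The documents give neither k nor N, so these inputs are assumptions:

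| k | N | k/N (points) |
|---|---|---|
| 1 | 80 | 1.3 |
| 2 | 50 | 4.0 |
| 3 | 50 | 6.0 |
| 3 | 30 | 10.0 |

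This is an upper limit for a given k, because it takes every affected subject to cross the threshold. As an example, take N = 50, k = 3 and an assumed rate as written of 20/50 = 40.0%. Non-response scoring gives 17/50 = 34.0%. Dropping the three subjects gives 17/47 = 36.2%, which removes only part of the overstatement.

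**Mean change.** If the other N − k subjects have mean m and the affected subjects have mean x, including the affected values shifts the mean by k(x − m)/N. For FEV1, take m = +12.37%, the 12-month figure from the earlier studies in Protocol Table 3. The documents give no x, so it is assumed:

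| k | N | assumed x | shift (points) |
|---|---|---|---|
| 3 | 50 | +50% | 3 × 37.63/50 = 2.3 |
| 3 | 50 | +100% | 3 × 87.63/50 = 5.3 |
| 2 | 50 | +150% | 2 × 137.63/50 = 5.5 |
| 3 | 30 | +200% | 3 × 187.63/30 = 18.8 |

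The result depends on assumed values of k, N and x. The table shows the mechanism and does not estimate the shift in this study.

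**The case against.** - **Inclusion is inferred from silence.** No sentence says post-procedure values count. A site might withdraw such a subject, and SAP 2.1 would then show the reason. This stands as a limit on the claim. It does not close the gap, because nothing requires withdrawal and the SAP has no effectiveness rule for the missing values that would follow.
- **The event may be rare.** Protocol 2.2 describes transplantation as little used, citing donor supply, low priority and patient age, and it presents LVRS as major surgery with risk. This stands, and it makes 3 of 30 an extreme case.
- **All observed values are a legitimate target.** In a descriptive, open-label study without a hypothesis (SAP 1.4), summarising outcomes whatever happened afterwards is defensible. The SAP does not say that this is its aim, and results presented as effectiveness of the Coil will be read as Coil effect.
- **Medians and adverse event listings help.** SAP 2.7 includes the median and maximum, and a few extreme values would hardly move the median. SAP 2.3.2.3 lists adverse events by subject with onset day, so a related hospitalisation may be visible. Neither corrects a responder rate.
- **Excluding values has its own bias.** If these subjects are Coil failures, removing them leaves a mean based on those who did better. This stands and shapes the fix.

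A reader might infer that a transplanted subject would normally meet all four responder definitions, or that mean FEV1 change would be inflated by up to about 20 points. The documents support neither: they give no effect size for any later procedure and no count of them.

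**Conclusion.** The gap is real and worth closing. Followed literally, the plan scores a subject on values measured after a later transplant, LVRS, lobectomy or other volume-reduction device, and such a subject could be counted as a Coil responder at any visit from 12 to 60 months. Each responder rate is overstated by up to k/N: 1.3 to 10 points on the assumed range, with the top end unlikely given what the protocol says about transplantation. The size and even the presence of a shift in mean change cannot be determined from the documents. The conclusion assumes that such subjects stay in follow-up and are measured. No type I error, power or success criterion is affected, because none is defined; what is at stake is how the durability results are read.

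**What to change.** Record on the eCRF the type and date of any lung transplant, LVRS, lobectomy or other volume-reduction device after treatment #1. In SAP 2.3.1:

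- Score the subject as a non-responder at all visits after that date, and keep the subject in the responder denominator.
- Present mean change in two ways, excluding post-procedure values and with all observed values, and state that exclusion may itself favour the Coil.
- Report the number and timing of these procedures by follow-up period.
- Keep these subjects in all safety tables.

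This is an analysis rule and changes no clinical management. It costs one eCRF field, one derived flag and an extra table. Late results may look slightly less favourable.
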